### Part II:

- Quantitative Endpoints: We will evaluate the performance of the application for detection of atrial fibrillation compared to a gold-standard ECG monitor. We will also evaluate adherence to the system and factors associated with adherence.
- Qualitative Interview Endpoint: Impact of app use on quality of life, anxiety, and selfactivation (using our questionnaire at baseline, at the 14-day follow-up, and the 44-day follow-up). This information will be obtained from study questionnaires administered at enrollment, at the end of Aim 2 at 14 days post-enrollment, and after study completion 44 days post-enrollment, as well as from exit interviews convened with up to 30 selected participants after they use the system.

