## Questionnaire-

### Part II (only):

At enrollment and at their 14-day follow-up study visits, all Part 2 participants will complete a questionnaire that includes standardized scales to assess quality of life (QoL), depression, anxiety, and self-activation. Questionnaires will take approximately 45 minutes to complete. If a participant does not return for a follow-up study visit or is unable to complete an in-person questionnaire assessment, then a phone call will be made to the participant to see if they are willing to complete the questionnaire via a phone assessment. These participants will still need to return their devices to receive compensation. We will permit phone calls and assist with return by mail on a case-by-case basis.

We will compare changes from baseline to the 14-day follow-up in these measures between the Aim 2 intervention (n=90) and Aim 2 control (n=30) groups.

At the end of each participant's 44-day enrollment, they will complete a questionnaire either over the phone or in person, whichever is easier for the participant, to assess QoL, anxiety, and self-activation. This questionnaire will take approximately 20 minutes to complete. Participants who were not randomly chosen to use the Pulsewatch system for 30 days (Aim 3 control group) will receive compensation upon completion of the 44-day follow-up questionnaire. Participants who were randomly chosen to use the Pulsewatch system for 30 days (Aim 3 intervention group) will receive compensation upon completion of the 44-day follow-up questionnaire and return of their devices.

We will compare changes from the 14-day follow-up to the 44-day follow-up in these measures between the Aim 3 intervention (n=60) and Aim 3 control (n=60) groups.

We will create a short-form questionnaire assessment in the event that a participant is unable to complete the full questionnaire. The only difference between the full assessment and short form is that the short form will contain only outcome measurements for the questionnaire. Here is an overview of the variables our questionnaires will be collecting. We have uploaded all of our questionnaires to eIRB.

Measurement	Questionnaire Tool	Outcome or Stratifier	Baseline Assessment (All Part II)	14-Days Follow-up Assessment (Control)	14-Days Follow-up Assessment (Intervention)	44-Days Follow-up Assessme nt (All Part II)
Physical asses		•	•			
Vision	Questionnaire (4 items)	Stratifier	✓			
Hearing	Questionnaire (3 items)	Stratifier	$\checkmark$			

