On the day of the participant's scheduled 14-day follow-up visit, a study team member will call the participant and complete the 14-day follow-up questionnaire. Upon completion of the questionnaire, the participant will be randomized into an Aim 3 arm. If the participant is randomized into the control arm for Aim 3, we will ask the participant to mail back all of their Pulsewatch devices via a prepaid package. We will then mail the participant their \$100 gift card. Our normal study protocol will be followed for the rest of these participants study period, which includes conducting a questionnaire over the phone 30 days later and mailing their \$50 gift card.

For participants randomized into the Aim 3 intervention arm, we will ask them to mail back their Cardiac Insight patches via a prepaid package. If the participant was in Aim 2 control and is now in Aim 3 intervention, we will mail them the Pulsewatch System and the AliveCor Kardia Mobile device. We will also mail them their \$100 gift card. If the participant was in Aim 2 intervention and is now in Aim 3 intervention, we will mail them the AliveCor Kardia Mobile device and their \$100 gift card. Upon receiving their devices, a study team member will conduct a phone call, or a Zoom call, with the participant to train them on their new devices. Our normal study protocol will be followed for the rest of these participants study period, which includes conducting a questionnaire over the phone 30 days later, mailing devices back via a prepaid box, and mailing the participant their \$50 gift card.

For participants who have agreed to complete an exit interview, the interview will take place over the phone upon completion of the participant's 14-day follow-up study visit. The fact sheet for this exit interview will be explained to the participant prior to completing the exit interview. We will include this fact sheet in the package we send to participants before completing their baseline interview, so the participant can have it to reference. If the participant misplaces the fact sheet, we will mail it to them again.

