## **AF Detection Analysis:**

Analysis for the study focus on the performance of daily wear of the Pulsewatch system for 9 hours compared to standard Cardiac Insight patch monitoring over the course of 14 days. We will examine the system's accuracy for pAF identification as well as estimation of AF burden. A participant will be classified as having pAF or not at the end of the 14-day monitoring period based on the gold standard monitor. Data from the Pulsewatch is divided into 30-second segments for analysis and a positive reading will be defined as AF being detected in at least 7 out of 10 continuous data windows (5 minutes). The total number of positive readings collected over 14 days from Pulsewatch will be used as the independent variable in a logistic regression to predict the binary outcome of pAF (yes vs. no). The area under the receiver operating characteristic (ROC) curve (AUC) will be calculated based on the results from the logistic regression to evaluate Pulsewatch performance for pAF screening. From the ROC curve, we can identify the cutoff point of total number of positive readings that produces the highest sensitivity and specificity combination.

Preliminary data suggest that Pulsewatch will have sensitivity, specificity and AUC of at least .9 to detect pAF. Assuming .

Similar analysis will be conducted using the % of positive readings among all readings collected from each participant as the independent variable. The 95% confidence intervals (CI) of the AUC will be calculated using formula given by Hanley and McNeil. We will then conduct exploratory analyses to examine whether characteristics affect watch performance over 14 days. For example, we will compare the area under 2 independent ROC curves of female vs. male participants (or vision impaired vs. not) using a chi-square test. At the end of 14-days we will review the data of 45 participants in Aim 2 intervention and see what % of participants have AF. If we see less than 5% of all participants using the devices have AF, we will have an adaptive protocol for analysis. We would ask participants to extend their use of the devices for an additional 14-days and continue to monitor the participants for potential AF cases. Their follow up assessment for participants in Aim 2 of Part II would be at the end of the 28 days if we take this approach.

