## Adherence Analysis:

In Aim 3 of Part II of the study, adherence will be operationalized to determine whether pulse recordings were present on each day over the 30-day period. We will examine whether participant characteristics, e.g., sex, cognitive impairment, or stroke-related quality of life, affect the likelihood of adherence over the 1-month study period. We will use a mixed effects logistic regression model, including the participant as the random effect to capture the correlation among repeated measures from the same participant, using participant characteristics as the fixed effects, and a binary indicator of daily adherence as the dependent variable. We will also examine the adherence time-trend by including time (day) as a fixed effect in the model and participant as a random effect to estimate the slope of adherence over time. To examine whether the time trend varies by participant characteristics, we will include the interaction between characteristics and time in the model so that the slope of adherence over time can be estimated for each category of participant characteristic variables and be compared among the categories (e.g., pAF diagnosed vs. no pAF). Secondary analyses will examine rates of adherence to Pulsewatch ECG prompts and will compare Pulsewatch users to the usual care group with respect to stroke-related quality of life, anxiety, and self-activation. We will calculate the change score between baseline and 1 month as a dependent variable. First, a t-test will be used to compare 2 study groups on the change score. We will use a linear regression model, which will include group indicator (Pulsewatch users vs. usual care) as the independent variable and possible confounders (e.g., medication adherence and participant demographics) as covariates, to estimate adjusted group differences on the change scores.

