The consent will include permission for follow-up contacts and medical record review, and will also request access to identified proxies, who would be able to help us contact patients in the event they change practices and do not follow up at UMMMC. We will offer modest incentives for recruitment and retention in Pulsewatch: T-shirts and/or bags and/or pens with Pulsewatch logos offered at recruitment and mailed during follow-up.

All participants will be brought back for a study visit approximately 14 days after enrollment. This visit will take place in a research area that is private and comfortable. There, participants will

return both of their patch monitors, smartwatch, and smartphone, and will complete a questionnaire. From the 120 participants in both the Aim 2 intervention and control groups, we will randomly select up to 60 participants to be offered an opportunity to self-monitor at home using the Pulsewatch smartwatch/smartphone for 30 days, as well as the AliveCor ECG recording device. The 60 participants who are randomized into the control arm of Aim 3 will not be offered the opportunity to self-monitor with any device. At the completion of the 30 days, participants in Aim 3's intervention group can either return for a follow-up visit to return all equipment and complete the 44-day follow-up questionnaire, or can return their devices through a prepaid package and complete the 44-day follow-up questionnaire over the phone. Participants in Aim 3's control group will have a choice to complete their 44-day follow-up questionnaire over the phone. Farticipants in Part II of the study will be sent a Fact Sheet reviewing all the details of the process (Fact Sheet: Part II Exit Interviews in eIRB submission). Upon receipt of the study equipment and/or the 44-day questionnaire, the study team will compensate the participants.

Compensation will be given as an incentive. All patients and caregivers who participate will be compensated for their time and efforts in the study as shown in the table below. Providers will not be compensated for participating.

Participant Sub-groups	Compensation	Time Earned					
	Amount						
Part I: Focus Group	\$60.00 gift card	After completing the focus group					
Care-givers	\$60.00 gift card	After completing the focus group					
Part I: Hack-a-thon	\$15/hour gift card	After completing the Hack-a-thon event					
Aim 2: Control group	\$100.00 gift card	After completing the baseline interview					

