## 25. LOCAL NUMBER OF SUBJECTS

There will be a total of up to 170 participants in this study.

Part I: Up to 40 out-patient stroke participants or caregivers and 10 providers. Part II: Up to 120 participants, including 30 in the Aim 2 control group and 90 in the Aim 2 intervention group. Of the 120 participants in both the Aim 2 intervention and control groups, 60 will be invited to participate in the intervention arm of Aim 3 and use the devices for 30 days. At the 14-day follow-up visit, the other 60 participants randomized into the control arm of Aim 3 will be invited to complete a questionnaire in person or over the phone at the end of 30 days.

In order to obtain 170 participants who complete the research, we may over enroll or replace participants who drop out.

Adaptive enrollment design (Part 2): If we struggle to identify sufficient numbers of eligible participants from the inpatient stroke service or clinics over the first 6 months of enrollment (<50% targeted enrollment), we will employ an adaptive design and approach patients presenting to UMMMC out-patient and in-patient cardiology and/or neurology clinics who have high risk for atrial fibrillation and stroke on the basis of a CHADSVASC score >=2. Furthermore, If we struggle to enroll a sufficient number of participants from the UMMS University campus, we will recruit at the stroke treatment centers at UMass Memorial - Health Alliance Hospital in Leominster, MA, and at UMass Memorial - Marlborough Hospital in Marlborough, MA. The PI has actively sought approval from these sites to approach patients from these locations in order to meet study enrollment goals.

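### The secondary Aim 3 patient-reported comparison needs one stated starting visit, the protocol's 60 vs 60 in the SAP's power statement, and the starting score named as a covariate

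*Protocol*

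**What the plan says.** **Starting point.** Protocol section 11 (Questionnaire, Part II only) states: "We will compare changes from the 14-day follow-up to the 44-day follow-up in these measures between the Aim 3 intervention (n=60"), with a control group of the same size. Protocol section 13 (Adherence Analysis) states: "We will calculate the change score between baseline and 1 month as a dependent variable". SAP Table 2 and the SAP's Aim 3 Analysis also run from baseline to one month. Protocol section 10 lists the assessments as separate occasions: "using our questionnaire at baseline, at the 14-day follow-up, and the 44-day follow-up". The questionnaire schedule in section 11 does the same.

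**Analysis.** Protocol section 13 and the SAP's Aim 3 Analysis plan a t-test on the change score first. A linear regression of the change score on group follows, with "possible confounders (e.g., medication adherence and participant demographics) as covariates". The starting value of the outcome is not among the examples.

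**Group sizes.** Protocol section 25 assigns 60 of the 120 Part II participants to the Aim 3 intervention arm, and refers to "the other 60 participants randomized into the control arm of Aim 3". Section 24 agrees, and sections 4 and 24 give the intervention number as up to 60. SAP Table 2 and the SAP's Aim 3 Power paragraph use 30 users and 30 controls, with 80% power for an effect size of .74 at 5% type I error.

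**Timing of allocation.** For COVID-19 visits section 11 is explicit: "Upon completion of the questionnaire, the participant will be randomized into an Aim 3 arm". For in-person visits the order of the day-14 questionnaire and Aim 3 allocation is not stated. If the low-AF extension in section 13 is used, "Their follow up assessment for participants in Aim 2 of Part II would be at the end of the 28 days".

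**Comparator.** Section 24 says: "The 60 participants who are randomized into the control arm of Aim 3 will not be offered the opportunity to self-monitor with any device". Sections 4 and 13 call this group usual care.

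**The concern.** Three features of one secondary analysis do not fit together.

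- The outcome has two descriptions. Change from enrolment covers 44 days and includes the Aim 2 period, when 90 of the 120 participants use Pulsewatch. Change from day 14 covers only the 30 days that Aim 3 randomises. Every completer has both starting scores, so the definition should be fixed in writing before the data are seen.
- The SAP's power statement describes a comparison half the size of the one the protocol will run. A reader relying on the SAP would misjudge what the comparison can detect.
- A score collected at the randomisation visit is the most obvious covariate for the same score 30 days later, yet no document names it. If it is left out, precision is lost.

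**Working it through.** **1. Which intervals can be computed?** Questionnaires fall at enrolment, day 14 and day 44 only. Enrolment to one month has no closing assessment. Enrolment to day 44 is 44 days. Day 14 to day 44 is 30 days, the length of the Aim 3 period. Only the last fits the one-month description, and it is the interval in section 11.

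**2. Reproducing the SAP's figure.** Inputs from the SAP: 30 per group, t-test, 80% power, 5% type I error. Two-sided testing is assumed because the SAP does not state sidedness.

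- Normal approximation: d = (1.960 + 0.842) × √(2/n). At n = 30 this is 2.802 × 0.258 = .72.
- Noncentral t: .736 at n = 30, which rounds to the SAP's .74. Power at .74 is 80.5%.
- A one-sided 5% test would give .65, so the SAP's figure is two-sided.

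The SAP's arithmetic is right for its own sample size.

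**3. The same calculation at the protocol's size (noncentral t).**

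| Completers per arm | Detectable effect (SD of change) |
|---|---|
| 60 | .516 |
| 57 (5% loss) | .529 |
| 48 (20% loss) | .578 |

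The loss rates are assumptions. The protocol gives none, and section 25 permits replacement of dropouts without promising it. A true effect of .74 has 98% power at 60 vs 60. A true effect of .516 has 50% power at 30 vs 30.

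**4. Gain from adjusting for the starting score.** Assume equal SDs at the two visits and a correlation r between starting and final scores. The documents give no r; .5 to .8 is assumed. In units of the SD of a single score:

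- SD of change = √(2(1 − r))
- residual SD after adjustment = √(1 − r²)
- variance ratio, adjusted to change = (1 − r²) / (2(1 − r)) = (1 + r)/2

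Detectable difference at 60 vs 60 = .516 × the relevant SD.

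| r | Variance ratio | Change score | Adjusted | Power of the change t-test at the adjusted figure |
|---|---|---|---|---|
| .5 | .75 | .516 × 1.000 = .516 | .516 × .866 = .447 | 68% |
| .6 | .80 | .516 × .894 = .461 | .516 × .800 = .413 | 71% |
| .7 | .85 | .516 × .775 = .399 | .516 × .714 = .368 | 73% |
| .8 | .90 | .516 × .632 = .326 | .516 × .600 = .309 | 76% |

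**5. Does the starting visit matter for precision?** If enrolment and day 14 correlate equally with day 44, it does not. Suppose day 14 correlates .7 with day 44, and enrolment .6 or .5. Change from enrolment then detects .46 or .52 raw SD, against .40 for change from day 14 and .37 with adjustment for day 14.

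**6. Is either change score biased?** Under the protocol, Aim 3 allocation is random across all 120 participants. The enrolment score precedes it, as does the day-14 score if it is taken before allocation. A simulation of that design used 90/30 in Aim 2, an independent 60/60 in Aim 3, a true Aim 3 effect of .30, and an Aim 2 effect of .30 at day 14 and .15 at day 44. With 6,000 runs for each of three correlation patterns, mean estimates were .30 to two decimals for change from enrolment, change from day 14 and the adjusted model. Adding Aim 2 arm to the adjusted model left its standard error almost unchanged, so that term is optional.

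**The case against.** The strongest reply is that section 11 already fixes the interval, and that section 13 sits in an Aim 3 paragraph about a 30-day period, where one month can only mean day 14 to day 44. On that reading, baseline is a loose word. This largely stands, and a reader who infers that the outcome definition is wide open goes further than the documents allow. But section 13 and the SAP are where an analyst will look, and neither says day 14.

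Four other stronger readings are tempting and not supported:

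- **That the t-test ignores the starting score.** It subtracts that score, with a coefficient fixed at 1. The regression's covariates are examples, so the score is not excluded either.
- **That change from enrolment is biased because it spans Aim 2.** Re-randomisation across both Aim 2 arms prevents this.
- **That the comparison is underpowered.** The SAP is dated 11/20/18 and the protocol has since acquired COVID-19 procedures, so 30 vs 30 looks like version lag. The change to 60 vs 60 is favourable.
- **That the SAP's 30 controls are the 30 Aim 2 controls.** The SAP does not say who they are.

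It is also fair to say that a t-test on change is valid in a randomised comparison, that the gain from adjustment is modest at high correlations, and that .52 is a best case requiring 60 completers per arm.

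**Conclusion.** The point holds as an inconsistency with a modest precision cost in a secondary analysis. It does not threaten validity.

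- The starting visit is day 14 in one section and an undefined baseline in another section and in the SAP. Day 14 is the likely intent.
- The SAP's .74 is correct for 30 vs 30 and out of date for 60 vs 60. The figure is .52 SD of the change score with 60 completers per arm, or about .53 to .58 with 5% to 20% loss and no replacement.
- Adjusting for the starting score cuts residual variance by 25% at r = .5 and by 10% at r = .8. This rests on equal SDs and an assumed correlation, but the direction holds for any r below 1.
- Using the day-14 score as a pre-randomisation covariate requires the questionnaire to come before Aim 3 allocation. The protocol says so only for COVID-19 visits.

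It should be fixed, because the corrections cost nothing and the SAP's power statement does not describe the planned comparison.

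**What to change.** 1. In Protocol section 13, SAP Table 2 and the SAP's Aim 3 Analysis, replace baseline with the Aim 3 randomisation visit, matching section 11: day 14, or day 28 if the low-AF extension is used. In the latter case also state when the final questionnaire falls.
2. Update the SAP to 60 vs 60, re-randomised at the end of Aim 2. Restate the detectable effect as .52 SD of the change score with 60 completers per arm, and give the figure under the assumed loss.
3. Make the planned linear regression the main analysis, with the same score at the randomisation visit as a named covariate. Aim 2 arm may be added. Change or final score may be the dependent variable: with the same starting score in the model, the arm estimate is identical.
4. State that the questionnaire is completed before Aim 3 allocation at in-person visits, as it already is at COVID-19 visits.
5. Minor wording: Protocol section 4 names self-efficacy as an Aim 3 outcome, but the day-44 questionnaire measures self-activation and not self-efficacy. Reconcile the two. Describe the comparator as using no study device during the 30-day period, since about 60 × 90/120 = 45 of the 60 will have used Pulsewatch in Aim 2.

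The cost is wording in both documents. The starting scores and Aim 2 arm are already collected, and no participants or questionnaire items are added unless the sponsor resolves item 5 by adding self-efficacy at day 44.

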## 14. Provisions to Monitor the Data to Ensure the Safety of Subject\*

Please review the Data Safety Monitoring Plan (DSMP) in the eIRB for a detailed description regarding human subject's protection.

This plan recognizes the nature of Part II of this study as a clinical trial and this Part involves more intensive data safety monitoring, including involvement of an independent monitor, [name]. The plan has been reviewed and approved by the Director of the Quantitative Methods Core, [name], who has extensive expertise in the design and conduct of clinical trials.

As outlined in the DSMP, we will employ an adverse event reporting system (see DSMP Report template in eIRB) that will be reviewed by the PI and the independent data study monitor to ensure safety of all enrolled participants. However, we have provided an overview of our analysis and management plan herein. For any incidental findings, the PI will review the recording of the pulse/ECG data and make a clinical decision; if necessary, the PI then will

Pulsewatch ISP V 1.5 Docket#: H00016067

